5.3. Administration

The product will be administered in accordance with the India LPD.

The recommended dosage of dacomitinib is 45 mg taken orally once a day at approximately the same time each day, until disease progression, participant refusal/lost to follow-up, or unacceptable toxicity occurs. Dacomitinib can be taken with or without food.

The participant should take dacomitinib the same time each day. If the participant vomits or misses a dose, he/she should not take an additional dose or make up a missed dose but continue with the next scheduled dose.

The dose of dacomitinib should be reduced for adverse reactions as described in Table 1. Dose modifications for specific adverse reactions are provided in Table 2.

Table 1. Dacomitinib Recommended Dose Reductions for Adverse Reactions

Dose level	Dose (Once a Day)
First dose reduction	30 mg
Second dose reduction	15 mg

Table 2. Dacomitinib Dose Modifications for Adverse Reactions

Adverse Reaction	Severity ^a	Dosage Modification
Interstitial lung disease	Any Grade	
Permanently discontinue dacomitinib.
Diarrhea	Grade 2	
Withhold dacomitinib until recovery to less than or equal to Grade 1; then resume dacomitinib at the same dose level.For recurrent Grade 2 diarrhea, withhold until recovery to less than or equal to Grade 1; then resume dacomitinib at a reduced dose.
	Grade 3 or 4	
Withhold dacomitinib until recovery to less than or equal to Grade 1; then resume dacomitinib at a reduced dose.
Dermatologic Adverse Reactions	Grade 2	
Withhold dacomitinib for persistent dermatologic adverse reactions; upon recovery to less than or equal to Grade 1, resume dacomitinib at the same dose level.For recurrent persistent Grade 2 dermatologic adverse reactions, withhold until recovery to less than or equal to Grade 1; then resume dacomitinib at a reduced dose.
	Grade 3 or 4	
Withhold dacomitinib until recovery to less than or equal to Grade 1; then resume dacomitinib at a reduced dose.
Other	Grade 3 or 4	
Withhold dacomitinib until recovery to less than or equal to Grade 2; then resume dacomitinib at a reduced dose.

^a NCI CTCAE Version 4.03.

If a participant cannot tolerate treatment after a dose reduction to 15 mg, treatment will be permanently discontinued.

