If a participant fails to recover within 2 weeks of interruption for a drug-related AE, treatment will be discontinued unless there is discussion of the clinical circumstance with the Sponsor and agreement that the participant may resume treatment after an interruption of greater than 2 weeks.

If a participant subsequently tolerates treatment well at the reduced level in the judgment of the investigator, the dose may be increased to the next dose level.

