9.6.1. Analysis of Primary Endpoint

The primary endpoint is the incidence of AEs. AEs will be summarized by type, frequency, severity (as graded by the investigator according to NCI CTCAE version 4.03 and coded by the Sponsor using MedDRA), timing, seriousness and relationship to dacomitinib. The focus of AE summaries will be on treatment-emergent AEs, those with initial onset or increasing in severity after the first dose of study medication. The number and percentage of participants who experienced any AE, SAE, treatment-related AE, or treatment-related SAE will be summarized descriptively. AEs leading to death or discontinuation of study treatment, events classified as Grade ≥ 3 , treatment-related events, and SAEs will also be summarized. Detailed information collected for each AE will be listed with a description of the event, duration, whether the AE was serious, intensity, relationship to study treatment, action taken, and clinical outcome.

Study Treatment Exposure

Drug exposure will be summarized using descriptive statistics. The number and percentage of participants with dose reduction, temporary/permanent discontinuations and the corresponding reasons will also be summarized. The number and percentage of participants with dose reductions/modifications and the corresponding reasons will also be summarized.

Laboratory Tests

Laboratory test results will be graded according to NCI CTCAE version 4.03. Data will be summarized by the type of laboratory test. Summary of laboratory abnormalities will be presented by maximum CTCAE Grade. For laboratory tests without an NCI CTCAE grade definition, results will be categorized as normal (within normal ranges), abnormal, or not done. Shift tables will be provided to examine the distribution of laboratory abnormalities.

Vital Signs

Vital signs data will be summarized using descriptive statistics (mean, standard deviation, median, quartiles, minimum, and maximum) of actual values and change from baseline for each nominal visit over time (ie, unscheduled assessments will be excluded).

Electrocardiograms

All ECGs obtained during the study will be evaluated for safety. The triplicate data will be averaged, and all summary statistics and data presentations will use the triplicate averaged data.

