3.4. Baseline Variables

Start and end dates of study treatment:

The date of first dose (start date) of study treatment is the earliest date of non-zero dosing of the study drug.

The date of last dose of study treatment is the latest date of non-zero dosing of the study drug.

Definition of baseline:

No windowing will be applied when defining baseline. Any deviations from the protocol specified window will be documented as protocol deviations. A separate definition of adequate baseline will be provided for antitumor activity endpoints.

For antitumor activity analyses and baseline characteristics associated with tumor assessments, the last assessment prior to date of the first dose of study treatment will serve as the baseline assessment.

For safety (including Eastern Cooperative Oncology Group (ECOG) performance status), the last assessment performed on or prior to date of the first dose of study treatment will serve as the baseline assessment. If there are no observations meeting these criteria, then baseline is considered missing.

Participants who start treatment and discontinue from the study on the same day may have two different sets of data collected on study day 1 (one during study and one in the End of Treatment (EOT) visit. Data reported at the EOT visit are not eligible for baseline selection.

Triplicate electrocardiograms (ECGs) are collected pre-dose; therefore the baseline for each ECG measurement is the average of the pre-dose measurements.

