6. ANALYSES AND SUMMARIES

6.1. Primary Endpoint(s)

6.1.1. Adverse Events

Analyses of adverse events will be conducted on the Safety Set and will include all data collected from the time of first dose to 28 days post last dosing date or the date prior to initiation of a new anticancer therapy, regardless of dosing interruptions or dosing compliance. All analyses will be based on treatment emergent events unless otherwise specified. Treatment emergent is defined in [Section 3.1](#). AEs not considered treatment emergent will be flagged in data listings.

A high level summary of adverse events will include the number and percent of participants with:

- Any Adverse Event;
- Serious AE;
- Adverse Events with CTCAE Grade 3-4;
- Grade 5 events;
- AEs associated with dose interruptions;

- AEs associated with dose reductions;
- AEs associated with withdrawal.

Additionally, the number of events reported for each of the categories above will be provided. Each unique adverse event at the Preferred Term (PT) level for a participant is included in the count.

Seriousness, toxicity grade, action taken (interruption, reduction, and withdrawal) are as reported by the investigator on the adverse event CRF.

Summaries by System Organ Class (SOC) and PT in decreasing frequency will be provided for:

- Treatment Emergent Events (All Causality);
- Treatment Emergent Events by Maximum Toxicity Grade (All Causality);
- Treatment Emergent Events (Treatment Related);
- Treatment Emergent Events by Maximum Toxicity Grade (Treatment Related);
- Serious Treatment Emergent Events (All Causality);
- Serious Treatment Emergent Events (Treatment Related).

An event will be considered treatment related if the investigator considered the event related to the study drug or if causality information is unknown.

The following summaries will be provided by PT only (ie, summaries will not include SOC) in decreasing frequency for:

- Treatment Emergent Events (All Causality) by Preferred Term and Maximum Toxicity Grade;
- Treatment Emergent Grade 3-5 Events (All Causality) by Preferred Term and Maximum Toxicity Grade;
- Treatment Emergent Adverse Events Leading to Dose Interruptions (All Causality);
- Treatment Emergent Adverse Events Leading to Dose Interruptions (Treatment Related);
- Treatment Emergent Adverse Events Leading to Dose Reductions (All Causality);
- Treatment Emergent Adverse Events Leading to Dose Reductions (Treatment Related);

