6.5.3.1. Exposure to dacomitinib

The summary of treatment exposure for dacomitinib will include the following information:

- Treatment duration (weeks);
- Cumulative dose (mg);
- Dose intensity (mg/week);
- Relative dose intensity (%).

The duration of dacomitinib (in weeks) is defined as:

$$\text{Treatment duration (weeks)} = (\text{last dose date} - \text{first dose date} + 1)/7.$$

The cumulative dose (mg) of dacomitinib is the sum of the actual dose levels that the participant received (ie, total dose administered (mg)).

The dose intensity (DI) and the relative dose intensity (RDI) of dacitinib will be calculated for each participant during the study. The DI (mg/week) of dacitinib is defined as:

$$DI \text{ (mg/week)} = [\text{cumulative dose (mg)}]/[\text{treatment duration (weeks)}].$$

The RDI of dacitinib is defined as the ratio of the DI and planned dose intensity (d) and expressed in %.

$$RDI \text{ (%)} = 100 \times [DI \text{ (mg/week)}]/[7 \times d \text{ (mg/week)}].$$

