6.5.3.2. Dose Reductions, Interruptions, and Delays

A dose reduction is defined as a non-zero dose that is less than the prior dose.

The number and percentage of participants with at least one dose reduction as well as a breakdown of dose reductions (1/2/3/ ≥ 4) will be summarized.

Reasons for dose reductions will also be summarized. Participants can contribute to more than one reason if multiple dose reductions occurred for different reasons, but will only be counted once per reason. Percentages will be calculated based on the total number of participants in Safety Set.

An interruption is defined as 0 mg dose administered on one or more days. (Note: A dose interruption is not considered a dose reduction). The number and percentage of participants with dose interruptions and the corresponding reasons will be summarized. Participants can contribute to more than one reason if multiple dose interruptions occurred for different reasons, but will only be counted once per reason. Percentages will be calculated based on the total number of participants in Safety Set.

The following defines how dose interruptions will be counted in the case of multiple dose interruptions:

- If an interruption occurs consecutively for at least two days due to the same reason, then it will be counted only once.
- If an interruption occurs consecutively for at least two days due to different reasons, then it will be counted for each reason
- If an interruption occurs for more than one day due to the same reason, but the days are not consecutive, ie. there is at least one dosing day in between, then each dose interruption will be counted as a different occurrence.

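### Would the undefined 'prior dose' in SAP 6.5.3.2 make the exposure table miss dose reductions that follow a hold?

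*SAP*

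**What the plan says.** SAP 6.5.3.2 gives two definitions. For reductions: "A dose reduction is defined as a non-zero dose that is less than the prior dose". For interruptions: "An interruption is defined as 0 mg dose administered on one or more days". A note adds that an interruption does not itself count as a reduction. Rules for counting repeated interruptions follow; the last treats two holds as separate only when a dosing day lies between them. Neither document defines the prior dose.

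Protocol 5.3 sets a starting dose of 45 mg once a day, with reduced levels of 30 mg and 15 mg in Table 1. A typical Table 2 instruction reads: "Withhold dacomitinib until recovery to less than or equal to Grade 1; then resume dacomitinib at a reduced dose". Later in the same section, if the reduced level is well tolerated, "the dose may be increased to the next dose level".

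Protocol 9.6.1 promises the output concerned: "The number and percentage of participants with dose reductions/modifications and the corresponding reasons will also be summarized". Separately, SAP 6.1.1 tabulates adverse events that led to reduction, and there the source is the site's own entry: "Seriousness, toxicity grade, action taken (interruption, reduction, and withdrawal) are as reported by the investigator on the adverse event CRF".

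SAP 6.5.3.1 also bears on the exposure summary. It says that relative dose intensity (RDI) "is defined as the ratio of the DI and planned dose intensity (d) and expressed in" per cent, and then divides by 7 × d, labelled mg/week.

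**The concern.** Calling a withheld day a 0 mg dose puts zeros into the dose series. The reduction sentence excludes zero for the current dose but is silent about zero for the dose it is compared with. Elsewhere the SAP is explicit when zeros are to be skipped: in 3.4, "The date of last dose of study treatment is the latest date of non-zero dosing of the study drug", and in 5.2.2 the cycle start requires a dose above zero. A programmer who took 6.5.3.2 record by record would compare the first resumed dose with 0 mg and find no reduction.

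That would not be a rare path. It is how every reduction in Table 2 comes about. At stake would be the number and percentage of participants with a reduction, the 1/2/3/≥4 breakdown and the reasons, in a study whose primary objective is safety and tolerability. The exposure table could also contradict the adverse event tables.

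A second, smaller worry is RDI. If d really were a dose intensity in mg/week, multiplying it by 7 would be wrong.

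**Working it through.** The plan states no figure for dose reductions, so there is none to reproduce. Its only design figure, a maximum standard error of 0.05 for an adverse event rate, does reproduce as √(0.5 × 0.5 / 100) = 0.05, but nothing here depends on it.

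**Inputs.** Dose levels 45, 30 and 15 mg (Protocol 5.3, Table 1). Withheld days recorded as 0 mg (SAP 6.5.3.2). Re-escalation allowed (Protocol 5.3).

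**How reductions arise.** Table 2 has five instructions that end in a lower dose: recurrent Grade 2 diarrhea, Grade 3 or 4 diarrhea, recurrent persistent Grade 2 dermatologic reactions, Grade 3 or 4 dermatologic reactions, and other Grade 3 or 4 reactions. All five withhold first.

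**Two counting rules.**
- Record by record: count a step if the dose is above 0 and below the record immediately before it.
- Last dose taken: count a step if the dose is above 0 and below the most recent dose above 0.

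| Dose sequence (mg) | Record by record | Last dose taken |
|---|---|---|
| 45-30 | 1 | 1 |
| 45-30-15 | 2 | 2 |
| 45-0-45 | 0 | 0 |
| 45-0-30 | 0 | 1 |
| 45-0-45-0-30 | 0 | 1 |
| 45-0-30-15 | 1 | 2 |
| 45-0-30-0-15 | 0 | 2 |
| 45-0-30-45-0-30 | 0 | 2 |
| 45-0-30-45-0-30-0-15 | 0 | 3 |

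Direct step-downs are counted alike. Only those that follow a 0 mg record are lost.

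**Participants.** The documents give no reduction rate, so R (participants per 100 with a reduction) and f (share of them whose every reduction follows a hold) are assumptions. The record-by-record table would show R × (1 − f).

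| R | f = 0 | f = 0.5 | f = 0.75 | f = 1 |
|---|---|---|---|---|
| 20 | 20 | 10 | 5 | 0 |
| 40 | 40 | 20 | 10 | 0 |
| 60 | 60 | 30 | 15 | 0 |

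**Which rule does the text support?** Three features of the documents point to the last dose taken.
1. The interruption rules in 6.5.3.2 contrast withheld days with dosing days. A 0 mg day is therefore not a dosing day, and the dose before a resumed dose is the one on the last dosing day.
2. Table 2 speaks of resuming at a reduced dose. Reduced has meaning only against the level before the hold.
3. The breakdown runs to three, four or more reductions. Table 1 has two steps down, so a third needs re-escalation. The word 'prior' is thus explained without any reference to 0 mg records: it follows the current level rather than the starting dose.

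**What does not depend on the definition.** Cumulative dose is the sum of doses, and dose intensity is that sum divided by duration. For 14 days at 45 mg, 7 days at 0 and 35 days at 30 mg, the sum is 630 + 0 + 1,050 = 1,680 mg over 8 weeks, or 210 mg/week. RDI is 210 / 315 = 66.7% under either counting rule.

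**RDI notation.** Full dosing is 7 × 45 = 315 mg/week. With d = 45 mg/day, RDI = 100 × 315 / (7 × 45) = 100%. With d = 315, it would be 100 × 315 / (7 × 315) = 14.3% for a participant who took every dose. The mg/week label on 7 × d already requires d to be a daily dose.

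**The case for a change.** The best case for a change is that the text does not settle the matter by itself. It calls a withheld day a dose. The qualifier 'non-zero' would be unnecessary if 0 mg records were not part of the series, and it is attached to only one side of the comparison. The note stops the 0 mg day from counting as a reduction but does not say what the resumed dose is compared with. The affected pathway is the protocol's standard one, and a single sentence would close the gap.

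Most of that is accurate. The term is undefined, and one available reading gives wrong counts. The argument from 'non-zero' elsewhere is weaker: in SAP 3.4 and 5.2.2 the qualifier stops a 0 mg record from shifting a date, and its absence here does not show that zeros were meant as comparators.

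The adverse event tables are not a full substitute either. They cover only reductions linked to an adverse event, they do not give the number of reductions per participant, and the documents do not show how the form records an event that led to both a hold and a lower dose. But every Table 2 reduction is for an adverse reaction, so the reductions at risk should largely appear there by a route that does not use 6.5.3.2. An exposure table near zero beside populated adverse event tables would be noticed at review.

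**Conclusion.** No change to the plan follows. SAP 6.5.3.2 leaves a term undefined, and analysts would fill it sensibly by comparing with the last dose taken. The section's own distinction between dosing days and 0 mg days supports that reading, as does the wording of Table 2. The other reading would leave the table without the very reductions the protocol is set up to produce.

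A miscount would need withheld days to be stored as separate 0 mg records and also used as comparators. The documents do not include the dosing form or the programming specifications, so neither can be confirmed. If both happened, the loss could reach every reduction that follows a hold; the participant figures above rest on assumed rates and show a range, not an expected loss. The damage would be confined to the count, percentage, breakdown and reasons in one descriptive table. Adverse event incidence, the adverse event tables on reductions, response rate, duration of response, cumulative dose, dose intensity and RDI do not use the definition. The study has no hypothesis test (Protocol 9.1) and no decision rule (SAP 5.1.2).

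The RDI point is a slip in naming d. The formula's units already fix it as the planned daily dose, and the wrong reading would give 14.3% at full dosing, which nobody would let pass.

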6.5.4. Concomitant Medications and Nondrug Treatments

The following analyses will be based on the Safety Set.

Concomitant medications are medications, other than study medications, which started prior to first dose date of study treatment and continued on on-treatment period as well as those started during the on-treatment period. Concomitant non-drug treatments refer to concurrent procedures, which were undertaken any time during the on-treatment period. Prior medications and prior non-drug treatments are medications/procedures which are started before the first dose of study treatment. Prior and concomitant medications will be coded in the WHO Drug coding dictionary. Prior and concomitant non-drug treatments will be coded with the most current version of MedDRA dictionary.

Summary of prior and concomitant medications will include the number and percentage of participants by Anatomical Therapeutic Chemical (ATC) Classification level 2 and preferred term. A participant will be counted only once within a given drug class and within a given drug name, even if he/she received the same medication at different times. If any prior or concomitant medication is classified into multiple ATC classes, the medication will be summarized separately under each of these ATC classes. The summary tables will be sorted on decreasing frequency of drug class and decreasing frequency of drug name in a given drug class. In case of equal frequency regarding drug class (respectively drug name), alphabetical order will be used. In case any specific medication does not have ATC classification level 2 coded term, it will be summarized under 'Unavailable ATC classification' category.

Summary of prior and concomitant non-drug treatments will include the number and percentage of participants by MedDRA's SOC and PT in descending order of frequency. Participants will be counted only once within an SOC or PT even if he/she received the same treatment multiple times.

6.5.5. Subsequent anticancer therapies

The following analyses will be based on the Safety Set.

Subsequent anticancer therapies are defined as medications/procedures entered in the 'Concomitant Medications' (with 'Category of Medication' = 'Follow-up Cancer Therapy'), 'Radiation Treatment' (with 'Subcategory' = 'Curative in intent'), and 'Non-drug Treatments' (with 'Category' = 'On-study Cancer Surgery' and 'Outcome of Procedure' = 'Resected' or 'Partially Resected') CRF pages. The number and percentage of participants within each category (medication therapy, radiation therapy, and surgeries) will be provided.

Medications will be coded using the WHO Drug coding dictionary and will be tabulated by preferred term in descending order of frequency.

6.6. Safety Summaries and Analyses

Summaries of safety parameters will be based on the Safety Set.

6.6.1. Laboratory Data

Laboratory results will be converted to International System of Units (Système International d'unités, SI) units which will be used for applying toxicity grades and for all summaries.

Quantitative data will be summarized using simple descriptive statistics (mean, Std Dev, median, quartiles, minimum, and maximum) of actual values and change from baseline for each nominal visit over time (ie, unscheduled assessments will be excluded). The total number of participants for change from baseline will include all participants who have both a baseline and a value at the nominal visit.

As described in [Section 3.4](#), baseline will be defined as the last assessment performed on or prior to date of the first dose of study treatment. If there are multiple assessments that meet the baseline definition on the same day without the ability to determine which was truly last, then the worst grade will be assigned as the baseline grade. Several of the CTCAE terms (including Hypo/Hypercalcemia, Chronic Kidney Disease, and Activated Partial Thromboplastin) can be derived using several laboratory tests (analytes).

Results collected as strict inequalities (eg, >10 , <10) will be converted to numeric values subtracting a factor of $<0.001>$. Expressions of the form " \geq " or " \leq " will be converted to the end point. These numeric values will be evaluated for clinically significant abnormalities, but will not be included in calculations of summary statistics.

Additionally, laboratory results will be programmatically classified according to NCI-CTCAE version 4.03 grade. Non-numerical qualifiers will not be taken into consideration in the derivation of grade (eg, hypokalemia Grade 1 and Grade 2 are only distinguished by a non-numerical qualifier and therefore Grade 2 will not be derived). In summary statistics the number and percentage of participants corresponding to grades that only include non-quantitative criteria will be displayed as a blank or NA (not assessed) rather than 0. If there is any overlap between grade criteria (eg, CTCAE grading criteria for Creatinine Increased – a value can fall into one range based on comparison to Upper Limit of Normal (ULN) and another range based on comparison to baseline), the highest (worst) grade would be assigned to that record. Grade 5 is defined in the CTCAE criteria guidance as an event with an outcome of death. Since laboratory data does not collect an outcome, Grade 5 is not used when programmatically grading laboratory data.

Grade 0 or Outside Toxicity Reference (OTR) is not defined specifically by in the CTCAE guidance. However, programmatically this is used as a category to represent those participants who did not meet any of the Grades 1 to 4 criteria. If the laboratory value is evaluable for CTCAE criteria grading (numeric value is present, valid units and ranges are present as required to allow conversion to standard units and grading), and does not qualify for any of the Grade 1-4 criteria for a given lab test, then the value is assigned as Grade 0 or OTR.

Several of the CTCAE terms (including Hypo/Hypercalcemia, Chronic Kidney Disease, and Activated Partial Thromboplastin) can be derived using several laboratory tests (analytes).

Abnormalities will be described using the worst grade by scheduled timepoint and overall. Worst case overall will be determined from scheduled and unscheduled visits. Several laboratory tests have bi-directional grading criteria defined so that both low (hypo) and high (hyper) values can be graded separately. Each criterion will be summarized separately. In the cases where a value is graded as a Grade 1, 2, 3, or 4 for one of the directions, that value will also be assigned as a Grade 0 for the opposite direction for that test. For example, a value meeting the criteria for Grade 3 Hypercalcemia will be classified as a Grade 0 Hypocalcemia. For CTCAE terms that can be derived using one of several laboratory tests, the maximum post-baseline grade for a given participant and CTCAE term will be the maximum across all possible laboratory tests.

Additional laboratory results that are not part of NCI-CTCAE will be presented according to the following categories by scheduled timepoint as well as overall: below normal limit, within normal limits, and above normal limits. In the unlikely event that for a given participant, clinically significant abnormalities are noted in both directions (eg, $>$ ULN and $<$ Lower Limit of Normal (LLN)), then both abnormalities are counted.

Liver function tests: Alanine aminotransferase (ALT), aspartate aminotransferase (AST), alkaline phosphatase (ALP), and total bilirubin (TBILI) are used to assess possible drug induced liver toxicity. The ratios of test result over the ULN will be calculated and classified for these three parameters during the on-treatment period.

Summary of liver function tests will include the following categories. The number and percentage of participants with each of the following during the on-treatment period will be summarized:

- $ALT \geq 3 \times ULN$, $ALT \geq 5 \times ULN$, $ALT \geq 10 \times ULN$, $ALT \geq 20 \times ULN$;
- $AST \geq 3 \times ULN$, $AST \geq 5 \times ULN$, $AST \geq 10 \times ULN$, $AST \geq 20 \times ULN$;
- $(ALT \text{ or } AST) \geq 3 \times ULN$, $(ALT \text{ or } AST) \geq 5 \times ULN$, $(ALT \text{ or } AST) \geq 10 \times ULN$, $(ALT \text{ or } AST) \geq 20 \times ULN$;
- $TBILI \geq 2 \times ULN$;
- Concurrent $ALT \geq 3 \times ULN$ and $TBILI \geq 2 \times ULN$;
- Concurrent $AST \geq 3 \times ULN$ and $TBILI \geq 2 \times ULN$;
- Concurrent $(ALT \text{ or } AST) \geq 3 \times ULN$ and $TBILI \geq 2 \times ULN$;
- Concurrent $(ALT \text{ or } AST) \geq 3 \times ULN$ and $TBILI \geq 2 \times ULN$ and $ALP > 2 \times ULN$;
- Concurrent $(ALT \text{ or } AST) \geq 3 \times ULN$ and $TBILI \geq 2 \times ULN$ and $ALP \leq 2 \times ULN$ or missing.

Concurrent measurements are those occurring on the same date.

Categories will be cumulative, ie, a participant with an elevation of AST $\geq 10 \times \text{ULN}$ will also appear in the categories $\geq 5 \times \text{ULN}$ and $\geq 3 \times \text{ULN}$. Liver function elevation and possible Hy's Law cases will be summarized using frequency counts and percentages.

An evaluation of Drug-Induced Serious Hepatotoxicity (eDISH) plot will also be created, with different symbols, by graphically displaying

- Peak serum ALT(/ULN) vs peak total bilirubin (/ULN) including reference lines at ALT= $3 \times \text{ULN}$ and total bilirubin= $2 \times \text{ULN}$.
- Peak serum AST(/ULN) vs peak total bilirubin (/ULN) including reference lines at AST= $3 \times \text{ULN}$ and total bilirubin= $2 \times \text{ULN}$.

In addition, a listing of all TBILI, ALT, AST and ALP values for participants with a post-baseline TBILI $\geq 2 \times \text{ULN}$, ALT $\geq 3 \times \text{ULN}$ or AST $\geq 3 \times \text{ULN}$ will be provided.

